## **7 STATISTICAL CONSIDERATIONS**

### **7.1 Review of Study Design**

An open-label, randomized, three-arm, directly observed therapy, pharmacokinetic study. HIV-uninfected non-pregnant cisgender women will be randomly assigned 1:1:1 to 1 of 3 dosing frequencies of DOT TAF-FTC: 2, 4, or 7 doses/week to help differentiate poor and modest from perfect adherence. Drug concentrations in blood, cervico-vaginal fluid, and tissue will be measured during the study.

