## 7.3 Data Analysis

### 7.3.1 Primary outcomes

**Primary outcome 1:** The goal is to describe the frequency of adverse events, including emergent HIV infection during the study period. We will conduct a descriptive analysis for meeting PrEP157 eligibility among participants. The distribution of demographics and graded adverse events will characterize by overall and study arms and proportions will be compared between study arms using chi-square statistics.

**Primary outcome 2:** The goal is to quantify the effect of dose on steady state TFV-DP in DBS and PBMC based on an incomplete block design.  $C_{ss}$  (drug concentration at steady state) will likely require a normalizing log transform, such that geometric means and CIs will be reported. Dose proportionality will be assessed using the power model (on the natural log scale)  $\ln(Y_{ijk}) = \mu + S_i + P_j + \beta \log(D_k) + \varepsilon_{ijk}$  (Eqn. 1). Where  $Y_{ijk}$  is the response,  $C_{ss}$ , for the  $k$ th dose ( $k=2, 4, 7$  doses/week),  $j$ th period ( $j=1,2$ ),  $i$ th subject ( $i=1, \dots, 45$ );  $\mu$  is the overall mean,  $S_i$  is a random subject effect,  $P_j$  is the period effect and  $\varepsilon_{ijk}$  is random error. Dose proportionality dictates that  $\beta=1$  for dose-dependent parameters and we will assume dose proportionality if the 90% CI is contained within the limits (0.8, 1.25). The SAS mixed procedure will be utilized for model (Eqn 1), again assuming a random subject effect. Although we do not anticipate a period effect, our design allows us to test this effect. For the primary analysis, we assume no effect of 'non-daily dosing' regimens; although this will be examined in a secondary analysis. If dose proportionality is not shown, we will examine proportionality separately for each of the "non-daily dosing" dosing regimens. If dose proportionality is still not demonstrated when adherence regimens are examined separately we will consider dose as a categorical predictor.

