### 7.3.2 Secondary outcomes

1. Examine models to predict non-daily adherence based on TFV/FTC and FTC-TP/TFV-DP in DBS.

We assume the modeling approaches of Aim-1. We will first consider a saturated model allowing a separate mean for each dose/adherence group. The results will then be compared to a reduced model with a class variable indicating non-daily dosing groups" or 100% dosing (that is, the effect of "non-daily dosing" adherence does not differ by dose groups). Drug concentration predictors of "non-daily dosing" will focus on TFV-DP in relationship to other drug moieties such as FTC-TP and FTC and TFV. For instance, the ratio of TFV-DP to FTC-TP may be used as a predictor of "2" versus "4" dosing per week. A proportional odds logistic approach which allows for an ordinal outcome and extensions which control for correlations between repeated measurements on a subject will be utilized in SAS or R statistical software. In addition, we will employ PK models (see Aim-1) to simulate TFV-DP to FTC-TP ratios for other dose regimens and estimate cut points for predicting non-daily dosing patterns.

2. Examine relationships among drug concentrations in plasma, RBC, DBS, and PBMC.

We will use mixed and non-linear mixed effects models to determine if concentrations in various matrices are related.

3. Evaluate the influence of demographics, biological on drug concentrations.

Kruskal-Wallis parametric test will be used to compare demographics and key study variables (e.g., age, pregnancy, HCT, contraception use, study arm, BMI, eGFR). Non-linear mixed effects models also will be used to probe covariate effects on PK. Secondary analyses are considered hypothesis generating and will not correct for multiple comparisons.

4. Compare drug concentrations in DBS from fingerstick versus transferring blood from blood tubes.

Since these are paired DBS samples, we will compute the ratio of TFV-DP in the two samples and a mixed model on the natural log of the ratio will be utilized to determine if CI is within 0.8 and 1.25, indicating equivalence. Bland-Altman analyses will also be evaluated.

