#### 7.4 Sample Size Considerations

The overall sample size was chosen to have up to 18 cisgender women in each relevant group (overall, n=54 non-pregnant cisgender women) sufficient to provide precise information on drug concentrations and to balance feasibility, efficiency, and provide robust TAF/FTC data in DBS for cisgender women. The sample size for drug concentration parameters is based on ensuring precision in the estimates to accurately describe the concentration kinetics of TAF/FTC in non-pregnant cisgender women and is consistent with multiple DOT PrEP studies done in US populations. The precision desired is a mean TFV-DP in DBS at steady state within  $\pm 15\%$  of the true population mean. The mean ( $\pm$  standard deviation) TFV-DP at steady-state in HIV-uninfected US cisgender men and cisgender women following directly observed doses of 25 mg TAF/200mg FTC once daily for 12 weeks was  $2381 \pm 601$  fmol/punches [coefficient of variation (CV) of 25%] (*Anderson et al*). Based on this variability and assuming average TFV-DP results are normally distributed, to be 90% confident that the DBS TFV-DP sample mean is within 15% of the true mean, a sample size of 15 participants is required for non-pregnant cisgender women with conservative assumptions. With the planned enrollment of 18 cisgender women per group for this study, even a 10% non-completion rate at 8 weeks of DOT therapy, we provide ample data to estimate steady-state means to within 10% in cisgender women.

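### The 0.8–1.25 limits sit on the power-model exponent without conversion for the 2–7 doses/week range, so the region called dose proportional covers dose-normalised ratios from 0.78 to 1.37

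*Combined protocol and SAP*

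**What the plan says.** Section 7.3.1, Primary outcome 2, sets the method: "Dose proportionality will be assessed using the power model (on the natural log scale"), with log steady-state concentration regressed on log dose and slope β. Proportionality is equated with β = 1, and the same sentence continues: "we will assume dose proportionality if the 90% CI is contained within the limits (0.8, 1.25"). The sentence does not say which quantity the interval belongs to, but β is the only parameter it names. If proportionality is not shown, the plan examines the non-daily regimens separately. If that also fails, it considers dose as categorical.

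Section 7.3.2, item 4, uses the same pair of numbers for fingerstick versus tube DBS. There a mixed model is fitted to the log of a concentration ratio "to determine if CI is within 0.8 and 1.25, indicating equivalence".

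The doses come from section 7.1: women are "randomly assigned 1:1:1 to 1 of 3 dosing frequencies of DOT TAF-FTC: 2, 4, or 7 doses/week". Section 7.4 bases the sample size on the precision of a mean. It gives neither power for the proportionality test nor a reason for these limits on β.

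**The concern.** The pair 0.8 and 1.25 is symmetric for a ratio, since 0.8 = 1/1.25. It is not symmetric for a slope centred on 1, where the distances are 0.20 and 0.25. What a given β means in concentration terms also depends on how wide the dose range is. The plan therefore uses one pair of limits on two different scales, and the tolerance it actually allows for proportionality is never stated.

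Dose proportionality is part of primary objective 2. A rule looser than intended makes it easier to report proportionality when concentrations depart from it by as much as section 7.3.2 would treat as the edge of equivalence. It also makes the fallback to regimen-specific and then categorical dose less likely to start.

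**Working it through.** **Inputs.** Doses 2, 4 and 7 per week, allocated 1:1:1 (section 7.1). Section 7.4: "The overall sample size was chosen to have up to 18 cisgender women in each relevant group", and a mean ± SD of 2381 ± 601, "fmol/punches [coefficient of variation (CV) of 25"% (601/2381 = 0.252). Section 7.4 also considers "even a 10% non-completion rate at 8 weeks of DOT therapy", about 16 per arm. The 90% CI corresponds to two one-sided 5% tests. The plan gives no derivation or power for this rule, so there is no figure of its own to reproduce first.

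**Step 1: what the limits on β mean.** Under the power model, the dose-normalised ratio of highest to lowest dose is r^(β−1), with r = 7/2 = 3.5.
- β = 0.80: 3.5^(−0.20) = 0.778, or 22% below proportional.
- β = 1.25: 3.5^(0.25) = 1.368, or 37% above proportional.

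**Step 2: limits on β that match a ratio of 0.80–1.25.** These are 1 ± ln(1.25)/ln(r). With r = 3.5: 1 ± 0.2231/1.2528 = 1 ± 0.178, giving 0.822 to 1.178.

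**Step 3: precision.** Assume one steady-state value per woman, parallel arms, no period term and the same variability in each arm.
- Log-scale SD = √ln(1 + 0.25²) = 0.246.
- Sum of squares of ln 2, ln 4 and ln 7 about their mean = 0.788.
- SE(β) = 0.246/√(18 × 0.788) = 0.065.
- With 52 df, t = 1.675 and the CI half-width is about 0.110.

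The whole interval must fit, so under the stated rule the point estimate must lie between about 0.91 and 1.14. That is an observed departure of roughly −11% to +19%.

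**Step 4: chance of declaring proportionality (simulated, CV 25%, 18 per arm).**

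| True dose-normalised ratio (β) | Stated limits 0.8–1.25 | Matched limits 0.822–1.178 |
|---|---|---|
| 1.25 (1.178) | 29% | 5% |
| 0.80 (0.822) | 9% | 5% |
| 1.37 (1.25) | 5% | below 1% |
| 1.00 (1.00) | 90% | 70% |

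For a true ratio of 1.25, acceptance under the stated limits is 38% at CV 20% and 23% at CV 30%.

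**Step 5: acceptance when truly proportional, in other cases.** At CV 25% and 16 per arm it falls from 0.86 to 0.62. At CV 30% and 18 per arm it falls from 0.75 to 0.46.

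**Step 6: dependence on the range.** For 4 versus 7 doses/week, r = 1.75. Fixed limits of 0.8–1.25 on β then mean ratios of 0.89 to 1.15, which is tighter than 0.80–1.25; matched limits would be 0.60 to 1.40. The same fixed limits are therefore too wide for one comparison and too narrow for another.

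**The case against.** **Size.** A reader might infer that a 37% departure would routinely be called proportional. It would not. The 37% is the upper edge of the region, the whole CI must fall inside, and a true 37% excess passes about 5% of the time, which is the nominal error rate. The lower edge is almost right (0.778 against 0.80; 9% against 5%). The looseness is therefore mainly for more-than-proportional accumulation, and the documents give no reason to expect that direction. All of this stands.

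**Consequence.** A reader might also infer that a false verdict would feed the adherence thresholds. Section 7.3.1 does not support that. Primary outcome 3 uses linear mixed models, 25th percentiles and ROC curves, none of them stated to be conditional on the verdict. Geometric means are reported in any case, and nonlinear mixed-effects models probe proportionality further. Passing the rule also does not fix β at 1. This too stands.

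**Reading.** The interval's parameter is not named, and the source cited for the power model was not available for this review. If a ratio was meant, the defect is one of wording, but it still needs correcting.

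**Assumptions.** Equation 1 describes two periods and 45 subjects, which does not match the 54-woman parallel design, so the SE above rests on a simplification. The CV is for daily dosing in DBS; variability in the other arms and in PBMC is not given. This limits the acceptance rates. It does not affect Steps 1 and 2, which depend only on the dose range.

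**Conclusion.** The point holds in a limited form. Read as written, the rule defines dose proportional as a dose-normalised ratio between 0.78 and 1.37 over 2–7 doses/week. This is asymmetric and wider than 0.80–1.25, with nearly all the excess on the upper side. The practical cost is about a 29% chance, instead of 5%, of declaring proportionality at a true ratio of 1.25, and 9% instead of 5% at 0.80. These rates assume CV 25%, 18 per arm and one steady-state value per woman.

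The effect is confined to the primary-objective conclusion on proportionality and to whether the fallback sequence in section 7.3.1 starts. It is worth correcting because this is the decision rule of a primary outcome and the change is small.

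**What to change.** In section 7.3.1, name the parameter and state the criterion on the dose-normalised ratio: proportionality is concluded if the 90% CI for r^(β−1) lies within 0.80–1.25, where r is the ratio of highest to lowest dose in the comparison. For 2–7 doses/week, r = 3.5 and the equivalent limits on β are 0.822 to 1.178. Recompute them for any comparison over another range, including those made when regimens are examined separately. Report the ratio with its CI whatever the verdict, and keep the existing fallback. If the sponsor prefers the wider limits, the plan should justify them in advance as ratios of 0.78 to 1.37.

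The wording change is about one line, but it makes the test harder to pass when proportionality is true, by the amounts in Steps 4 and 5: from about 0.90 to 0.70 in the base case, with the lowest figure 0.46 at CV 30%. The plan claims no power for this test, so no stated power is lost, but the SAP should now give the expected chance of passing.

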In addition to the power model, we will utilize nonlinear mixed effects models using PK software (NONMEN and/or ADAPT-5) to model drug concentration over time on drug. For this analysis, all available drug concentration samples will be utilized, thereby accounting for missed doses due to protocol deviations. Change in objective function and/or AIC will be used to compare models. This approach will be used to further probe dose proportionality and the final model(s) will be used as a basis for simulation studies.

**Primary outcome 3:** The goal is to identify TFV-DP cut points associated with adherence levels. For the primary analyses, we will attempt to discriminate adherence for 2, 4 and 7 dosing based upon TFV-DP. As above, we will combine the "non-daily dosing" regimens. Linear mixed models with random intercepts, 25th percentiles, and receiver operating characteristics curves will be used to generate predicted concentration thresholds for varying dosing frequency (ranging from 1 to 7 doses/week) for each matrix-analyte pair. Analyses will be adjusted for age, contraception use, study arm, BMI, eGFR, and hematocrit.

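### Primary outcome 2 lets failure to show proportionality, not misfit of the power model, lead to categorical dose, and its planned non-daily effect cannot be told from curvature

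*Combined protocol and SAP*

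**What the plan says.** The design compares "3 dosing frequencies of DOT TAF-FTC: 2, 4, or 7 doses/week" in parallel arms. For Primary outcome 2, Section 7.3.1 fits the power model (Eqn 1), in which log steady-state concentration is linear in log dose with slope β, and sets this rule: "we will assume dose proportionality if the 90% CI is contained within the limits (0.8, 1.25").

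Two fallbacks follow. The first begins "If dose proportionality is not shown, we will examine proportionality separately for each of the" non-daily regimens. The second is conditional on the first and discretionary: "If dose proportionality is still not demonstrated when adherence regimens are examined separately we will consider dose as a categorical predictor".

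The primary analysis assumes no effect of non-daily dosing, "although this will be examined in a secondary analysis".

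Section 7.3.1 gives no check of whether Eqn 1 fits, and does not say that an estimated slope other than 1 would be kept for prediction. It does add nonlinear mixed-effects models, compared by objective function or AIC. Primary outcome 3 separately produces "thresholds for varying dosing frequency (ranging from 1 to 7 doses/week) for each matrix-analyte pair".

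**The concern.** Two questions are treated as one. The first is whether concentration is proportional to dose, that is, whether β is close to 1. The second is whether the power model describes the data, that is, whether log concentration is linear in log dose. The CI rule answers only the first. A slope of 0.9, or a wide interval around 1, leaves the power model valid, yet either can lead to categorical dose. A correct model for a primary outcome could then be set aside because of an imprecise or mildly non-unit slope. Estimates from Eqn 1 at frequencies that were not studied would go with it.

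The planned non-daily analysis has a related difficulty. Only the 7/week arm is dosed daily, so with three arms there is no information left to separate an effect of intermittent dosing from curvature in the dose relation. Curvature could be reported as an effect of the dosing pattern.

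**Working it through.** **The plan's own figures.** Section 7.4 gives no power or precision for β. Its only sample-size result is 15 women per group for a mean within 15% with 90% confidence. The stated inputs give (1.645 × 0.25 / 0.15)² = 7.5, so 8 women, or 10 with the t distribution. The conservative assumptions behind 15 are not given. This figure does not enter the check below.

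**Inputs.** Doses 2, 4 and 7 per week (Section 7.1). 18 women per arm: "With the planned enrollment of 18 cisgender women per group for this study". About 16 per arm after non-completion: "even a 10% non-completion rate at 8 weeks of DOT therapy". CV 25% for TFV-DP in DBS (Section 7.4). Assumptions: parallel arms, one steady-state value per woman, and exactly log-linear data, so that the power model is true. Eqn 1 as printed has two periods and 45 subjects, which does not match this design. The design was followed.

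**Precision of β.**
- Log SD: σ = √ln(1 + 0.25²) = 0.246.
- x = ln 2, ln 4, ln 7 = 0.693, 1.386, 1.946; mean 1.342; Sxx = 0.788.
- SE(β) = σ / √(18 × 0.788) = 0.065.
- 90% half-width = 1.675 × 0.0654 = 0.110 (t, 52 df).
- To pass, the estimate must lie between about 0.91 and 1.14.

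**How often the overall criterion fails although the model is true (simulation).**

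| True β | 18 per arm, CV 25% | 16 per arm, CV 25% |
|---|---|---|
| 1.00 | 10% | 14% |
| 0.95 | 27% | 32% |
| 0.90 | 56% | 59% |
| 0.85 | 81% | 82% |

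Hand check at 18 per arm: for β = 0.9, Φ((0.91 − 0.90)/0.065) ≈ 0.56. For β = 1, the lower tail is about 0.08 and the upper about 0.02, together 0.10.

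The PBMC CV is not given. If it were 35%, 40% or 50%, failure at β = 1 would be 43%, 61% or 89%.

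**The by-regimen step.** The plan does not define it. It is read here as 2 versus 7 and 4 versus 7.
- 4 versus 7: half-width 1.691 × 0.246 × √(2/18) / ln(7/4) = 0.248. The interval is then about 0.50 wide against a window of 0.45, and it passes in about 1.5% of trials even at β = 1.
- 2 versus 7: half-width 0.111, so it mostly repeats the overall result.
- At β = 0.9, failure overall and then also by regimen is 54 to 56%, a change of about one percentage point or less. The most lenient variant (each pair uses its own variance and one pass is enough) gives about 53%.

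**Cost of categorical dose at 4/week (log scale, CV 25%).**
- Power model: SE = σ√(1/54 + (1.386 − 1.342)²/(18 × 0.788)) = 0.034; 90% half-width 5.6%.
- Categories: SE = σ/√18 = 0.058; 90% half-width 9.7%. There is no estimate at 1, 3, 5 or 6 doses/week.

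**Aliasing of the non-daily effect.** The contrast c = (0.807, −1.807, 1) on the three log means is zero for an intercept and for any slope in ln(dose), so it is the single degree of freedom for curvature. Applied to the non-daily indicator (1, 1, 0) it gives 0.807 − 1.807 = −1. The non-daily coefficient is therefore that curvature contrast with its sign changed. SE = 0.246 × √((0.807² + 1.807² + 1²)/18) = 0.129; 90% half-width 0.216, that is ×/÷ 1.24.

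**Power of a 5% test of that contrast (18 per arm, CV 25%).** If the 4/week mean lies 10% above the line through the other two arms, the shift is 1.807 × ln 1.10 = 0.172 and power is about 26%. At 15% above, the shift is 0.253 and power is about 49%.

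**The case against.** The strongest reply is that the text is milder than it may look. A reader might infer that the power model is dropped whenever proportionality is not shown. That is not what Section 7.3.1 says: there is a step in between, and the last step is only to be considered. This stands as a matter of wording. The intermediate step rescues few trials under the reading used here, however, and the discretion leaves a choice after the data on a primary outcome with no stated criterion.

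A reader might also infer that the trial loses its ability to interpolate between 2, 4 and 7 doses per week. The documents do not support this. The nonlinear mixed-effects models are fitted in addition to the power model and feed the simulations. Primary outcome 3 has its own tools for 1 to 7 doses per week. Neither depends on the proportionality verdict.

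The harm to the benchmarks is modest. A half-width of 9.7% at 4/week is still within the ±15% target and the 10% statement of Section 7.4. Arm-specific means, an endpoint in Section 7.2, are estimated without bias by categories. Repeated weekly sampling could also lower the effective variability below that of one value per woman.

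Finally, the non-daily term added to Eqn 1 is numerically the missing lack-of-fit test, so in that form the check would be made under another name. That is correct. It is not used to choose the model, though, and its label invites a wrong attribution. A rule that kept the power model whenever this test was non-significant would have the opposite weakness, given its power of 26 to 49%.

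**Conclusion.** The point holds in a limited form. The route to categorical dose is failure to show β near 1, which is not evidence against the power model. In DBS, at the plan's own CV and with a correct model, the overall criterion fails in about 10% of trials at β = 1 and 56% at β = 0.9 (14% and 59% at 16 per arm). A mildly non-unit slope is thus the main route there, and imprecision alone the lesser one.

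For PBMC, 43 to 89% at CV 35 to 50% is an assumed range. It would be tempting to say that PBMC is the noisier matrix, but the documents give no PBMC variability.

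The consequence is confined to Eqn 1: lower precision and no estimates between the studied doses from that model. Separately, and whatever the variability, three arms cannot identify a non-daily effect apart from curvature in Eqn 1.

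The failure rates rest on parallel arms, one steady-state value per woman and exact log-linearity. The size of the by-regimen rescue also rests on the reading of that undefined step.

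**What to change.** In Section 7.3.1, Primary outcome 2:

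1. Report β with its 90% CI as the proportionality verdict (shown, not shown or inconclusive), define the three outcomes against the limits, and state that the verdict does not choose the model.
2. Do not abandon the power model with estimated β merely because the CI is not inside the limits. In all cases, report its fit next to the arm-specific geometric means, with the one-degree-of-freedom departure from log-linearity and its CI. Base any move to categorical dose on the size of that departure and its CI. A non-significant test alone should not count as evidence of fit.
3. Report the non-daily contrast from Eqn 1 as departure from log-linearity, and state that it cannot be attributed to intermittent dosing.

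The cost is a few sentences and one contrast. Study conduct and sample size do not change. The departure will be imprecise (×/÷ 1.24 at CV 25%), so some judgement remains, but it would be made on the quantity that bears on model fit.

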## 2.3 Primary Objectives

- 1) To describe the safety of TAF-FTC-based PrEP in HIV-uninfected cisgender women.
- 2) To define the cisgender women-specific expected blood concentrations and dose-proportionality for TFV-DP in DBS and PBMCs in cisgender women using directly observed TAF-FTC therapy at 2, 4, 7 doses per week.

- 3) To establish a model to predict adherence rate to TAF-FTC by level of TFV-DP in DBS for cisgender women.

[figure not shown]

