### **7.2 Study endpoints**

- **Aim 1:** Mean, variance, and dose proportionality for TFV-DP or TFV in plasma, DBS, and PBMC for 2, 4, 7 of DOT TAF-FTC dosing per week.
- **Aim 2:** Prediction model of adherence rate by level of TFV-DP in DBS.

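### Primary outcome 3 plans TFV-DP thresholds and a 2/4/7 discrimination, but no doses/week estimate, prediction interval or stated misclassification, although objective 3 promises a model that predicts adherence

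*Combined protocol and SAP*

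**What the plan says.** Section 2.3 gives primary objective 3 as: "To establish a model to predict adherence rate to TAF-FTC by level of TFV-DP in DBS for cisgender women". Section 7.2 repeats it as the Aim 2 endpoint: "Prediction model of adherence rate by level of TFV-DP in DBS". In both, concentration goes in and adherence comes out.

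Section 7.3.1, Primary outcome 3, words the aim differently: "The goal is to identify TFV-DP cut points associated with adherence levels". It then describes two things.

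- A classification step: "we will attempt to discriminate adherence for 2, 4 and 7 dosing based upon TFV-DP".
- A set of thresholds, from linear mixed models with random intercepts, 25th percentiles and ROC curves: "receiver operating characteristics curves will be used to generate predicted concentration thresholds for varying dosing frequency (ranging from 1 to 7 doses/week".

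The covariate sentence follows: "Analyses will be adjusted for age, contraception use, study arm, BMI, eGFR, and hematocrit".

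Section 7.3.2, secondary outcome 1, does contain a model with adherence as the outcome. Its purpose is "Examine models to predict non-daily adherence based on TFV/FTC and FTC-TP/TFV-DP in DBS" and its method is "A proportional odds logistic approach which allows for an ordinal outcome". The same section calls secondary analyses hypothesis generating.

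Section 7.4 sizes the trial for the precision of mean TFV-DP. It says nothing about the error of a predicted adherence rate.

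**The concern.** The protocol says that its results will be used to interpret drug levels in other PrEP studies. A user of those results starts from a measured DBS value and wants to know how many doses per week it implies, and how surely. A threshold table answers the reverse question: what concentration to expect at a given dosing frequency. If only thresholds are published, a value near the 4-dose level will tend to be read as 4 doses/week, with nothing to show how far off that could be.

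The adjustment for study arm adds to the difficulty. Arm is the assigned number of doses per week, so it is the quantity to be predicted. It is unknown for a future user. As a factor alongside ln(doses/week), it would also absorb the dose slope, because three arms correspond one to one with three doses.

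**Working it through.** **Is there a figure in the plan to reproduce?** None concerns predicted adherence. The nearest is the 15 women per group in section 7.4, for a mean within 15% at 90% confidence. The printed inputs give (1.645 × 0.25 / 0.15)² = 7.5, so 8 women (10 with the t distribution). The plan mentions conservative assumptions without listing them. The figure concerns a mean and does not bear on this point.

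**What each analysis delivers**

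| Analysis | Input → output | Status | Error specified |
|---|---|---|---|
| Objective 3 / Aim 2 (promised) | TFV-DP → adherence rate | primary | – |
| Mixed model and 25th percentiles (7.3.1) | dose → concentration threshold | primary | none stated |
| ROC discrimination (7.3.1) | TFV-DP → 2, 4 or 7 | primary | sensitivity and specificity implied; reporting not stated |
| Proportional odds (7.3.2) | drug moieties → ordinal adherence | secondary, non-daily dosing | none stated |

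No row gives a primary doses/week estimate with its prediction error.

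**How large that error could be (illustration)**

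Inputs from the documents:
- TFV-DP 2381 ± 601, stated as CV 25% (section 7.4; US men and women on daily dosing)
- 18 women at each of 2, 4 and 7 doses/week (section 7.5)
- slope 1, the dose-proportional case of Eqn 1 (section 7.3.1)

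Assumptions: the same CV in all arms, one steady-state DBS value per woman, log-normal values.

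1. Log SD: s = √ln(1 + 0.25²) = 0.246.
2. Design: mean of ln(dose) = (0.693 + 1.386 + 1.946)/3 = 1.342. Sxx = 18 × (0.421 + 0.002 + 0.365) = 14.18.
3. 90% half-width on the log scale at dose d: k = t(0.95, 52) × s × √(1 + 1/54 + (ln d − 1.342)²/Sxx).
4. At d = 4: k = 1.675 × 0.246 × 1.009 = 0.416. The interval is 4 × exp(±0.416) = **2.6 to 6.1 doses/week**.
5. The same formula gives 1.3 to 3.0 at d = 2, and 4.6 to beyond 7 at d = 7.
6. Misclassification at a log-midpoint cut:
   - 4 versus 7: Φ(−½ ln(7/4)/s) = Φ(−0.280/0.246) = **13%** in each direction.
   - 2 versus 4: Φ(−0.347/0.246) = 8%.

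The unrounded CV (601/2381 = 25.2%, s = 0.2485) gives 2.63 to 6.09 and 13%.

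| CV | 90% interval at the 4-dose mean | 4 v 7 error | 2 v 4 error |
|---|---|---|---|
| 20% | 2.9 to 5.6 | 8% | 4% |
| 25% | 2.6 to 6.1 | 13% | 8% |
| 40% | 2.1 to 7.7 | 23% | 18% |

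The planned threshold methods need not agree. At s = 0.2485 the 25th percentile of the 7-dose arm lies at the level expected from 7 × exp(−0.674 × 0.2485) = 5.9 doses/week. The 4-versus-7 log-midpoint lies at √(4 × 7) = 5.3. The plan does not say which one prevails.

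**The case against.** A reader might infer that the plan produces nothing but concentration cut points and no measure of error at all. The text does not support that. Primary outcome 3 sets out to separate the three regimens on the basis of TFV-DP and names ROC curves. That runs from concentration to dose group, and an ROC curve is made of sensitivity and specificity. A 25th-percentile threshold also has a known error by construction: a quarter of that dosing group falls below it. Secondary outcome 1 has an ordinal adherence outcome, allows for repeated measures and adds simulation from the PK models. It is not confined to drug ratios, which are given there only as an example.

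It can also be argued that the complaint is about format. The Protocol Schema defines the primary outcome as benchmark concentrations and the dosing frequency that generates them. A classifier is a legitimate prediction model, and thresholds for successive dosing frequencies can serve as a lookup table.

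Much of this stands, and it is why the planned cut points should be kept. What remains is that objective 3 and Aim 2 speak of an adherence rate. A three-way split does not give one, and a lookup table without error does not show how well it is known. Reporting of sensitivity and specificity is left unstated. The secondary model, given its status and its focus on non-daily dosing, cannot carry a primary objective.

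**Conclusion.** The point holds as a gap in specification. The primary analysis of objective 3 lacks a doses/week estimate for an observed concentration, a prediction interval, and a commitment to report misclassification. The thresholds and the ROC discrimination are sound as far as they go.

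The figures of 2.6 to 6.1 doses/week and 13% are illustrative and should not be read as forecasts for this trial. They carry a US daily-dosing CV over to Kenyan women in all three arms and assume slope 1. The plan does not say whether that CV covers the within-woman variation of a single DBS value; if it does not, the interval would be wider. At a CV of 20% the interval at the 4-dose mean still runs from 2.9 to 5.6.

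A reader might also infer, from the remark about combining non-daily regimens, that the 2- and 4-dose arms will be pooled and cannot be separated. The wording is too unclear to conclude that, and the same paragraph plans to discriminate 2 from 4, so this point does not rest on it.

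**What to change.** In section 7.3.1, Primary outcome 3:

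1. Keep the ROC and percentile cut points, and state that sensitivity, specificity and misclassification will be reported for each.
2. Add inverse prediction from the steady-state log-log power model (Eqn 1), fitted without study arm as a covariate. For an observed concentration y, report doses/week = exp((ln y − a)/b), with a and b the fitted intercept and slope. Give a 90% prediction interval that includes between-woman variance, within-woman variance and parameter error. The weekly DBS samples allow both variance components to be estimated.
3. Report this over the studied range of 2 to 7 doses/week, and label anything below 2 as extrapolation, including the planned 1-dose threshold.
4. If the power model fails and dose is treated as categorical, as section 7.3.1 foresees, there is no slope to invert. Report class probabilities for 2, 4 and 7 doses/week instead.

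The cost is SAP wording and a little extra analysis. No new data, visits or participants are needed. The drawback is a visibly wide interval, but that is information the users of the benchmark need.
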